Biodentine new bioactive calcium silicate-based cement has been recently launched in the dental market as a 'dentin substitute'. This new biologically active material facilitates its penetration through opened dentinal tubules to crystallize interlocking with dentin and provide mechanical properties. Biodentine has been developed using MTA based cement technology and hence; added improved properties such as physical qualities and handling, and its wide range of recommended applications in endodontic repair and pulp capping. [16]

Radiographic imaging of the dentoalveolar complex has been assessed using conventional periapical radiography, the benchmark for intraoral radiographic imaging for decades. Their known limitations of image magnification, distortion, superimposition and overlap of anatomy always led to unclear and misrepresentation of structures. Although the advent of digital intraoral radiography didn't improve these limitations, it provided a more active image manipulation than the film-based radiographs and reduced patient exposure

substantially. [17, 18]

7 - Objectives and hypothesis:

The objective of this prospective randomized clinical trial is to compare the clinical / radiographic outcomes of MTA and Biodentine as pulpotomy biomaterials used in apexogenesis treatment of symptomatic / asymptomatic vital immature mandibular permanent first molars with carious pulp exposure.

8-Trial Design:

Randomized clinical trial (RCT), parallel groups with 1:1 allocation ratio, Triple blinded (patient, clinical and radiographic assessor of the results and statistician)

III- Methods:

9-Study settings:

This study will be carried out on patients attending the outpatient clinic in Pediatric Dentistry department, Faculty of Dentistry, Cairo University, Egypt. the procedures will be carried out by [name] Associate Professor of Pediatric Dentistry in Pediatric Dentistry clinic. expected time duration from 2017 to 2018.

10- Eligibility criteria:

Inclusion criteria:

- Medically free children.
- Bilaterally Symptomatic / asymptomatic vital immature mandibular first permanent molars (with clinical carious exposure of the pulp and presence of bleeding upon exposure)
- Patients with an age range from 7-8 years.
- Absence of sinus tract, soft tissue swelling.

The exclusion criteria:

- Molars were excluded if non-restorable.
- excessive mobility (more than 1 mm horizontally).

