All patients attending the outpatient clinic in pediatric dentistry department complaining from carious mandibular first permanent molars will be screened and enrolled in the study if they meet the eligibility criteria.

16- Allocation:

Sequence generation:

Access cavity prepared molars will be assigned into experimental or control group using simple randomization 1:1 by the help of the computer software(random.org).

Allocation concealment mechanism:

Numbered opaque sealed envelopes.

Implementation:

The child will choose an envelope randomly and open it after caries removal so that the operator knows which pulpotomy agent will be used only after finishing the access cavity. Sequence generation will be done by the third author and the patient assignment will be done by the operator.

17- Blinding:

Patients and their parents, the assessor and the statistician will be blinded.

18- Data collection methods:**Primary outcome:**

Clinical assessment of the following findings:

1. postoperative pain: through asking the child and the parent if there is pain either continuous or intermittent
2. Swelling: through visual examination by the assessor either intraorally or extra-orally.
3. Sinus or fistula through visual examination of the gingiva by the assessor.
4. Tooth mobility: By the back of the mirror checked by the assessor to detect mobility in any direction

This assessment will be conducted every follow-up visit throughout the study period at baseline, 6, 12 and 18 months.

Secondary outcome

Radiographic assessment to detect stage of root development, crown: root ratio, apical closure and presence of radiolucency through standardized periapical radiograph by parallel technique using film holder. This assessment will be conducted every follow-up visit throughout the study period at baseline, 6, 12 and 18 months.

Postoperative records will be performed by the assessor to avoid individual variability and to promote data quality.

19- Data management:

Explanation to the parents about the importance of the follow-up visits in addition to treatment of other dental problems are plans to promotes participants retention and complete the follow-up. Also, phone calls before the dates before the next follow-up visit will be scheduled.

All findings will be documented in the examination sheet then transferred electronically to computer in secured lace sequentially.

20- statistical methods:

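### The child opens the envelope that reveals the pulpotomy agent, which contradicts the claimed patient blinding, and no rule keeps the numbered envelopes in order or traceable

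*Combined protocol and SAP*

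**What the plan says.** All references are to the combined protocol and SAP.

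- **Section 16, sequence generation:** molars are assigned "using simple randomization 1:1 by the help of the computer software(random.org".
- **Section 16, concealment:** "Numbered opaque sealed envelopes".
- **Section 16, implementation:** "The child will choose an envelope randomly and open it after caries removal", with the stated purpose "so that the operator knows which pulpotomy agent will be used only after finishing the access cavity". The same paragraph has the third author generate the sequence and adds that "the patient assignment will be done by the operator".
- **Section 8:** "Triple blinded (patient, clinical and radiographic assessor of the results and statistician".
- **Section 17:** "Patients and their parents, the assessor and the statistician will be blinded".
- **Section 18, primary outcome:** postoperative pain is collected "through asking the child and the parent if there is pain either continuous or intermittent". The Section 12 table lists spontaneous pain within the primary outcome, recorded by questionnaire.

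Nothing in these sections says that the card carries a code, that it is kept from the child or parent, that envelopes are opened in number order, or that the number opened is recorded.

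**The concern.** Two stated properties of the trial depend on what happens with the envelope.

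The first is patient blinding. The person who opens the envelope is one of those declared blind, and is later a source for a primary outcome component. If the child knows the material, the pain answer is no longer protected from that knowledge, and the trial could not accurately be reported as patient-blinded.

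The second is the link between the random list and the children treated. Numbering normally serves to fix the order of use, so that anyone can later check each allocation against the list. If any envelope may be picked, the numbering no longer does this unless the number is recorded some other way. The trial could not then show afterwards that each allocation was the first and only one drawn.

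**Working it through.** The plan gives no figure on this point, so the check sets the passages side by side.

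**Patient blinding**

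1. Who opens the envelope: the child (Section 16, implementation).
2. What opening it discloses: the agent, since the stated purpose of the timing is that the operator learns it only then (same sentence).
3. Who is declared blind: the patient in Section 8; the patient and parents in Section 17.
4. Is there a step that would reconcile 1 and 2 with 3, such as a code only the operator can read or a card passed unread? None is described in Sections 8, 16, 17 or 18.
5. Does an outcome depend on it? Yes. Pain is asked of the child and the parent (Section 18) and is a primary component (Section 12). Swelling, sinus tract and mobility are examined by the assessor, so for those items the child's knowledge matters less directly.

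Steps 1 to 3 conflict as written. For the parent the conflict is weaker: the text does not place the parent at the opening, so parental unblinding would require the parent to be present or the child to pass the information on.

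**Sequence and audit trail**

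1. The list is computer-generated, 1:1, by simple randomization.
2. The envelopes are numbered, opaque and sealed.
3. The child may choose any of them. The envelope opened by the k-th child need not be number k, so the order of the list does not determine who receives which agent.
4. Is chance allocation lost? No. The contents are hidden at the moment of choice, and a free draw from sealed envelopes is still random.
5. Is traceability specified? No. The plan does not say that the number is written against the child's code or the tooth, that opened envelopes are kept, or that they are reconciled with the list. It also names the operator as making the assignment while the child does the choosing, without saying how the two fit together.

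**Unit of allocation**

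Section 8 describes parallel groups. Section 20 calls the study split-mouth, Section 10 requires bilateral involvement, and Section 16 assigns molars. Under a split-mouth design, a child who knows the agent on one side knows it on the other by elimination, and then reports pain for both. Under parallel groups, the child knows one agent only. A record of the envelope therefore needs the tooth or side as well as the child's code, and the plan must say how many molars one envelope settles.

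**Effect on the sample size**

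None. Section 14 uses success rates of 90% and 50%, alpha 0.05, 80% power and 15% drop-out. No input concerns the envelope procedure, so 20 per group, raised to 20 × 1.15 = 23, is unchanged by the fix.

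**The case against.** The strongest defence is that the documents are silent rather than wrong. They do not say what is printed on the card or whether the child reads it. A child of 7 or 8 may make nothing of a product name, and nothing suggests that children or parents prefer one of these materials. This limits how far the point can go, but it does not remove the contradiction: the plan asserts blinding, has the blinded person open the disclosure, and describes nothing in between.

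A reader might infer several stronger things that the documents do not support.

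- **That allocation concealment is lost.** The envelopes are opaque and sealed and are opened only once the access cavity is finished, so their contents are unknown at the choice. What is missing is order of use and an audit trail.
- **That a second draw could never be detected.** The envelopes are numbered and Section 27 provides coded IDs, so a reconciliation could in principle be made. The supported statement is that no such check is described.
- **That parents are unblinded.** Their presence at the opening is not described.
- **That the pain result would move by some number of points, say 5 to 10.** No passage gives a rate at which knowing the material changes an answer, or a direction. Such a figure would be invented. Even taken at face value, it would be one eighth to one quarter of the 90 − 50 = 40 point difference the trial is sized for.

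One further objection stands. The third author generates the sequence (Section 16) and is also named as examiner in the Section 12 table. Changing who opens the envelope does not settle that overlap, which needs its own answer.

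**Conclusion.** The concern holds in limited form. Section 16 as written contradicts the patient blinding claimed in Sections 8 and 17, and so leaves that blinding unsecured for self-reported pain within the primary outcome. Separately, the numbered envelopes are not required to be used in list order, and no safeguard is described that links an envelope to a child or tooth or that would expose a re-draw.

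The size of any resulting bias cannot be given from the documents, and bias itself is not shown. The conclusion assumes that the card names the agent in a form the child could read or hear; a coded card would remove the blinding conflict, but none is mentioned. The finding on order and traceability does not depend on that assumption. The plan should be changed on this point because the conflict touches a primary component and the correction is nearly free.

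**What to change.** Replace the implementation sentence in Section 16 with wording to this effect:

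*After the access cavity is finished, a team member other than the outcome assessor writes the child's code, the tooth or side, and the date on the next envelope in numerical order. That person then opens it out of the sight of the child and parent and shows the card to the operator only. The opened envelope is kept on file. Each envelope settles [one molar / both molars of a child].*

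The bracket must be completed consistently with whichever design, parallel-group or split-mouth, the protocol adopts in Sections 8 and 20. The sentence giving the assignment to the operator should be aligned with the new text.

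If the child is to go on opening the envelope, withdraw the patient-blinding claim in Sections 8 and 17. That makes the text honest about blinding but leaves the order and traceability gap open, so the recording steps would still be needed.

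The cost is a short rewrite of Section 16 and a few seconds per allocation, with no change to the sample size. It assumes a suitable team member is available at the chair; the documents name no assistant, so this should be confirmed. If the protocol is already approved, the change may need a formal amendment under Section 25.

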- Radiographic evidence of peri- and /or inter-radicular lesions, internal/ external root resorption, pulp/ canal calcifications.

IV- Intervention:

Diagnosis:

1. Full history data will be collected, including personal, medical and previous dental data
2. Clinical examination using mirror and probe to assess the inclusion criteria.
3. Radiographic examination using preoperative digital periapical radiograph to assess the inclusion criteria.
4. Preoperative photograph will be taken.

Operative procedure:

Experimental group:

1. Injection of local anesthesia and rubber dam isolation.
2. caries and roof of the pulp chamber will be removed by a fissure diamond bur (Diatech, Heerbrug, Switzerland) and high-speed handpiece with coolant.
3. The pulps will be amputated to the orifice level using a long-shank diamond round bur.
4. Haemostasis will be achieved by gentle placement of a saline-moistened cotton pellet over amputated pulps for 5–10 min.
5. Calcium silicate-based BiodentineTM (Septodont Ltd., Saint Maur des Fausse's, France) will be mixed according to the manufacturer's instructions, radicular pulp will be covered by the material using a wet cotton pellet.
6. A self-cure glass ionomer (GC; GC Corporation, Tokyo, Japan) will be placed over the pulpotomy agent as a final restoration.
7. Immediate post-operative radiograph and photograph will be taken.

Control group:

The same procedures will be carried out as the experimental group, but the pulp stumps will be covered with fast-setting mineral trioxide aggregate (MTA) ENDOCEM MTA (Maruchi, Wonju, Korea) and will be prepared according to the manufacturer's instructions. A 3-mm-thick layer of MTA will be placed over the amputated pulps and will be gently adapted to the dentinal walls using a wet cotton pellet. A self-cure glass ionomer (GC; GC Corporation, Tokyo, Japan) will be placed over the pulpotomy agent as a final restoration.

Postoperative care:

Instructions to avoid lip and cheek biting in addition to oral hygiene measures.

Follow up:

Assess the outcomes clinically and radiographically at (baseline, 6, 12 and 18 months).

Criteria for discontinuing or modifying intervention:

In case of an unsuccessful outcome after pulpotomy, the molars will be managed by other pulp therapy techniques or extraction.

Strategies to improve adherence to intervention:

Explanation to the parents about the importance of follow up visits in addition to treatment of other dental problems.

Concomitant care:

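### Section 16 lets the unblinded operator know the material during pulp amputation and haemostasis, although the arms first differ only at the next step

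*Combined protocol and SAP*

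**What the plan says.** Section 16 states both what is assigned and when. On sequence generation: "Access cavity prepared molars will be assigned into experimental or control group using simple randomization 1:1". On implementation, the child picks an envelope and is to "open it after caries removal so that the operator knows which pulpotomy agent will be used only after finishing the access cavity". It adds that "the patient assignment will be done by the operator".

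Section IV, Operative procedure, gives the order of work. Step 2: "caries and roof of the pulp chamber will be removed by a fissure diamond bur". Step 3: "The pulps will be amputated to the orifice level using a long-shank diamond round bur". Step 4: "Haemostasis will be achieved by gentle placement of a saline-moistened cotton pellet over amputated pulps for 5–10 min". Step 5 is the mixing and placement of the covering material. The control group follows the same procedure with MTA in place of Biodentine.

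Section 17 lists who does not know the arm: "Patients and their parents, the assessor and the statistician will be blinded". The operator is not listed. Section 9 describes one operator for all procedures.

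**The concern.** The trial asks what the covering material does on pulp stumps prepared in the same way. Everything up to step 5 is common preparation and can be done without knowing the arm. Section 16 already defers disclosure for this kind of reason, but the deferral is tied to caries removal and the access cavity, which is only part of the common preparation.

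Two things are at stake. First, an operator who knows the material may, without intending to, carry out steps 3 and 4 differently by arm. The range of times in step 4 leaves more room for this than the amputation level, which is fixed. Blinded follow-up protects the measurement of the outcome, but it cannot correct a difference in preparation. Second, a molar that is allocated but not carried through to step 5 would be lost with its arm known. The plan does not say how such a molar would be handled.

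**Working it through.** No arithmetic applies. The plan gives no figure on this point, so the check sets the texts side by side.

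| Operative step (Section IV) | Same in both arms? | Position relative to opening (Section 16) |
|---|---|---|
| 1. Anaesthesia and rubber dam | Yes | Before |
| 2. Caries and chamber roof removed | Yes | Before: caries removal and the finished access cavity are the stated triggers |
| 3. Amputation to the orifice level | Yes | Not stated; opening beforehand is allowed |
| 4. Haemostasis, 5–10 min | Yes | Not stated; opening beforehand is allowed |
| 5. Material mixed and placed | No, first difference | After |

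1. **Earliest opening.** Section 16 uses two markers, caries removal and a finished access cavity. Step 2 removes the caries and opens the chamber. Amputation has its own number and a different bur. The natural reading is that the envelope may be opened between steps 2 and 3.
2. **Latest opening.** None is given. The timeline in Section 13 lists allocation, access preparation and placement of the material at the same time point. It has no row for amputation or haemostasis, so it does not settle the order.
3. **Need to know.** The control-group text changes only the covering material and its placement. Nothing in steps 3 or 4 depends on the arm.
4. **Who acts.** One operator, not listed as blinded, carries out the steps and makes the assignment.
5. **Molars that do not reach step 5.** The discontinuation rule in Section IV concerns an unsuccessful outcome after pulpotomy. Section 20 defines no analysis set. No text covers an allocated molar in which the pulpotomy is not completed.
6. **Number of draws.** Section 8 says parallel groups, Section 20 says split-mouth, and Section 10 asks for bilateral molars. If one draw fixes both molars of a child, opening it for the first reveals the material for the second before that tooth's access cavity is begun.

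**The case against.** The strongest reply is that the documents nowhere say the envelope is opened before amputation. Section 16 sets an earliest point and no latest one, Section IV does not use the term access cavity, and an operator could comply by opening after haemostasis. This stands: opening before step 3 is the natural reading and is permitted, but it is not an explicit instruction.

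A reader might also infer more than the text supports:

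- *That the operator judges, with the arm in view, how far to amputate and whether bleeding is controlled.* The level is fixed at the orifice, and no judgement of haemostasis is described. The only bleeding criterion is an eligibility item in Section 10, assessed on exposure.
- *That molars will be excluded by arm for uncontrolled bleeding.* No text removes or reroutes a molar on that ground. The point is only that the plan is silent about a molar that is not completed.
- *That the loss can be counted.* The documents give no rate of failed haemostasis. The 46 in Section 14 are subjects, and the number of molars is unsettled while the design statements conflict.

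It is also fair that the plan already limits the risk. The written steps are identical in both arms, the envelopes are opaque and sealed, and the assessor is listed as blinded. The operator must know the material from step 5 in any case, so bias at placement would remain. These points reduce the concern. They do not give a reason to disclose the arm two steps earlier than needed.

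**Conclusion.** The concern holds in a limited form. As written, the allocation rule permits the unblinded operator to know the material during steps 3 and 4, which are common to both arms. This is an avoidable route for performance bias and for loss of a molar after its arm is known. Neither is shown to occur, and the size of any effect cannot be derived from the documents. The conclusion rests on reading the numbered steps as the order of work and on taking the end of step 2 as the point at which caries removal and the access cavity are complete. If the authors already intend opening after haemostasis, the same change simply records it. This is a cheap improvement that should be made, not a flaw that invalidates the design.

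**What to change.** Change Section 16 so that the envelope is opened only after step 4 is finished and immediately before the material is mixed. Reword the sentence on sequence generation so that the molars assigned are those that have completed step 4, not those with only an access cavity. Leave the clinical steps, the eligibility criteria and the way an envelope is chosen as they are. Report any molar that does not reach step 5 as not randomised, with the count. Add the opening point to the timeline in Section 13.

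The practical cost is small: the envelope is opened later in the same visit, and step 5 already places mixing after haemostasis. There are two downsides to state:

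- The randomised set is limited to molars that reach step 5, so the results apply to those molars.
- Under a split-mouth design with one draw per child, the change protects only the first molar unless both are prepared before opening. A molar that does not reach step 5 would also leave its partner unpaired, so the plan would need to say how such a child is handled. Sections 8 and 20 must therefore be reconciled before the new wording is fixed.

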All data will be collected, checked, revised, tabulated and entered into the computer. Qualitative data will be presented as frequencies and percentages. Since the study is a split-

mouth design; Wilcoxon signed-rank test will be used to compare between the two groups. Friedman's test will be used to study the changes by time within each group. Kaplan-Meier survival curve will be constructed to calculate the mean survival estimates of the two groups. Comparison between survival times will be performed using Log rank test.

The significance level will be set at $P \leq 0.05$. Statistical analysis will be performed with IBM® SPSS® Statistics Version 20 for Windows.

21-Monitoring:

The study data and results will be monitored regularly by the assessor who will have full access to these data.

22- Harms:

No reported adverse effects for both testing pulpotomy agents. Any adverse events appear during the trial will be recorded, documented and treated.

23-Auditing:

Auditing of the study design will be done by the evidence-based committee, Faculty of Dentistry -Cairo University.

V- Ethics and dissemination:

24-Research ethics approval:

This protocol and the template informed consent form will be reviewed by the Ethics Committee of Scientific Research - Faculty of Oral and Dental Medicine - Cairo University.

25-Protocol amendments:

Any modification to the protocol which may have an impact on the conduction of the study, potential benefit of the patient or my affect patient safety including, the changes of study objectives, study design, sample size or significant administrative aspects will require a formal amendment to the protocol.

26-Consent and Assent:

Researcher will discuss the trial with legal guardian of each participating child. They will be able to have an informed discussion with the researcher after explaining the procedure in simple words. Verbal assent will be taken orally from the participating child while written consent will be taken from the legal guardian of each participating child who is willing to participate in the

® IBM Corporation, NY, USA.

® SPSS, Inc., an IBM Company.

trial. All consent forms will be translated into Arabic.

27-confidentiality:

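### Sections 8, 16 and 20 disagree on the design, and if the trial is split-mouth, Section 16 does not secure concealment for a child's second molar

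*Combined protocol and SAP*

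**What the plan says.** The protocol describes its design in four places, and they do not agree.

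- Section 8: "Randomized clinical trial (RCT), parallel groups with 1:1 allocation ratio".
- Section 14 sizes two groups of subjects, 20 per group, raised to 23 per group (46 in total) for drop-out.
- Section 16, sequence generation: "Access cavity prepared molars will be assigned into experimental or control group using simple randomization 1:1". The implementation paragraph gives the aim of the procedure as "so that the operator knows which pulpotomy agent will be used only after finishing the access cavity". A single draw is described, made by the patient once the decay has been cleared. The operator makes the assignment.
- Section 20 calls the study split-mouth: "mouth design; Wilcoxon signed-rank test will be used to compare between the two groups".

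Section 10 requires "Bilaterally Symptomatic / asymptomatic vital immature mandibular first permanent molars (with clinical carious exposure of the pulp and presence of bleeding upon exposure". Section 17 lists patients and parents, the assessor and the statistician as blinded. The operator is not on that list. The Section 13 timeline puts the eligibility screen, clinical examination and preoperative radiograph under enrolment, and access preparation under allocation.

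The protocol does not say whether there is one envelope per child or per molar, how the second molar gets its material, which molar is treated first, whether both are treated at one visit, or whether both cavities are finished before an envelope is opened.

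**The concern.** Section 16 aims at a sound safeguard: the operator should not know the material until the tooth has been opened. It is written for one tooth. In a split-mouth trial of two materials, each child receives both, so whatever the first molar receives determines what the second will receive. If the first molar has been allocated before the second is opened, the operator opens the second knowing its material.

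This matters because one eligibility criterion, "with clinical carious exposure of the pulp and presence of bleeding upon exposure", is seen only when the tooth is opened. The person who judges it is the unblinded operator, who also makes the assignment. A second molar could be declared ineligible, or handled differently, with its material known. Under a paired test, losing one molar loses the pair. Selective loss of this kind would bias the comparison of materials, and the trial report would not show it unless exclusions were logged by assigned material.

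**Working it through.** **1. The plan's own sample size.** Inputs from Section 14: success 90% and 50%, alpha 0.05 (taken as two-sided), power 80%. For two independent proportions without continuity correction, with mean proportion 0.70:

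n = [1.960 × √(2 × 0.70 × 0.30) + 0.842 × √(0.90 × 0.10 + 0.50 × 0.50)]² / 0.40² = [1.270 + 0.491]² / 0.16 = 19.4, so 20 per group.

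Power at 20 per group is 81.3%, and 20 × 1.15 = 23. The stated figure is reproduced, by a formula for independent groups. This fits Section 8 and not the pairing in Section 20. The point below does not depend on the sample size.

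**2. What each reading of Section 16 implies.**

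- *One molar per child (Section 8).* There is no second molar, so concealment works as described. The split-mouth statement and paired test in Section 20 are then wrong.
- *Split-mouth, one draw per child, both cavities finished before the envelope is opened.* Molars opened with the material known: 0%.
- *Split-mouth, one draw per child, molars opened one after the other.* One molar in two is opened with the material known: 23 of 46 if 46 counts molars, or 46 of 92 if 46 counts children. Either way 50%.
- *Each molar draws its own envelope by simple randomization.* The first draw reveals nothing about the second. The chance that a child receives both materials is 2 × 0.5 × 0.5 = 0.5, so 11.5 of 23 children, or 23 of 46, are expected to receive both. The other half receive the same material twice and give no within-child contrast for the paired test.

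So within a split-mouth trial with one draw per child the exposed share runs from 0% to 50%. Separate draws avoid the disclosure but break the planned analysis.

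**3. Possible size of the bias.** None of these inputs is in the documents: 30% of pulps are poor; success is 60% in poor pulps and 95% in good ones; the materials do not truly differ; pulp quality is independent between a child's two molars; each material comes second in half of the children. The operator removes a share f of the poor second molars, with their pairs, only when one particular material is due.

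Base success = 0.7 × 0.95 + 0.3 × 0.60 = 0.665 + 0.180 = 0.845.

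Success in the affected arm = [0.845 + 0.665 + 0.180 × (1 − f)] / [1 + (1 − 0.3f)]:

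- f = 25%: (0.845 + 0.800) / 1.925 = 0.855, a shift of about 1.0 point.
- f = 50%: (0.845 + 0.755) / 1.85 = 0.865, a shift of 2.0 points.
- f = 100%: (0.845 + 0.665) / 1.70 = 0.888, a shift of 4.3 points.

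The other arm stays at 0.845, because under independence the partner molars removed with the pairs are a random sample. The pairs lost are 7.5%, 15% or 30% of those in which that material comes second.

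A second set of assumptions gives a similar size. If both materials have 90% success and a share f of the 10% failure-prone second molars is dropped in the same way, the shifts are 1.1, 2.3 and 4.7 points.

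**The case against.** A reader might infer that half of the molars are in fact opened and judged eligible with the allocation known. The documents do not support that. It needs one draw fixing both molars, and a second molar opened after the envelope. Neither is written. Section 16 speaks of molars already prepared, which permits both cavities to be finished first, and its simple randomization, read literally, permits a separate draw for each molar. Fifty per cent is the upper end of a range.

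A reader might also infer that all of Section 10 is judged with the material known, including the exclusion "Molars were excluded if non-restorable". That is too broad. Section IV (Diagnosis) assesses inclusion by clinical and radiographic examination, the Section 13 timeline places these checks before allocation, and no step judges restorability again at access. What mainly remains open is the exposure and bleeding criterion, together with operative handling. The protocol describes no exclusion of a molar after allocation, so the selective-removal mechanism is hypothetical.

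On size, averaging first and second molars with equal weight would give shifts of 1.0, 2.2 and 5.3 points, but that counts removed pairs as still present. The figures that allow for pair removal are 1.0, 2.0 and 4.3. They would be smaller if pulp quality is similar within a child, because poor molars then leave the other arm too. All are small beside the 40-point difference assumed in Section 14.

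Finally, Section 8 says parallel groups, and on that reading the point does not arise. This limits the point but does not remove it: Section 20 states the split-mouth design outright, Section 10 asks for bilateral molars, and on neither split-mouth reading does Section 16 as written secure both concealment for the second molar and a valid paired test.

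**Conclusion.** The point holds in conditional form. Sections 8, 16 and 20 cannot all stand. If the trial is split-mouth with both materials in each child, the concealment that Section 16 states is not secured for the second molar: from 0% to 50% of molars can be opened, and their exposure and bleeding confirmed, by an unblinded operator who knows the material, depending on an order of work that the protocol does not give. If each molar draws separately, about half of the children are expected to receive both materials and the paired test does not fit.

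The possible bias is modest: about 1.0 to 4.3 points under the assumptions above, with the top figure requiring every poor second molar to be discarded in one arm. It should be corrected because the remedy is cheap and the safeguard is one that the protocol already claims. Nothing in the documents shows that such selection is planned or expected.

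**What to change.** Reconcile Sections 8, 14, 16 and 20 on the design and the unit of randomisation. If the trial is split-mouth:

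- In Section 16, randomise the side within each child, with one envelope per child stating which side receives which material.
- Open the envelope only after the Section 10 criteria, including exposure and bleeding, have been confirmed and logged for both molars.
- Where the second exposure can be confirmed only at a later sitting, count the child as randomised with both molars when the envelope is opened. Log any later exclusion with its reason and assigned material, and report these exclusions by material.
- In Section 20, analyse all randomised molars with a pre-specified method that accepts incomplete pairs, so that losing one molar does not remove the other.

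If the trial is one molar per child, remove the split-mouth statement and the paired test from Section 20, and this point falls away.

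The cost is revised wording, one column in the log and a little analysis work. Some children will be found ineligible before the envelope is opened instead of after it.
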